2.2 SCREENING EVALUATION

Step 1: The following assessments may be performed as soon as the initial 1st line treatment cycles with platinum/pemetrexed are administered.

- NCI LP confirmation of diagnosis
- NCI LP determination of mesothelin expression
- Medical History and Physical Examination

Step 2: Once mesothelin expression and diagnosis are confirmed, then proceed with the following tests described below.

The following screening assessments will occur within 28 days prior to initiation of study therapy:

- Medical history and physical examination including vital signs
- ECOG Performance Status
- CT scan of chest, abdomen and/or pelvis and areas of known or suspected disease involvement; MRI may also be performed when appropriate
- FDG-PET scan
- Echocardiogram
- Electrocardiogram
- Viral markers HBsAg, anti-HCV, anti-HIV

The following screening assessments will occur within 21 days prior to initiation of study therapy:

- Ophthalmologic exam (within 3 weeks before start of study therapy)
 - Visual acuity (BCVA according to ETDRS, or Snellen, or Landolt C or other charts)
 - Measurement of ophthalmic pressure (IOP)
 - Dry eye test [Schirmer test]
 - Slit lamp

The following screening assessments will occur within 7 days prior to initiation of study therapy:

- CBC with differential; Acute Care Panel (sodium, potassium, chloride, bicarbonate, creatinine, glucose, urea nitrogen, eGFR); Hepatic Panel (alkaline phosphatase, ALT, AST, Total Bilirubin, Direct Bilirubin)
- PT, PTT
- Urinalysis
- β-HCG in women of childbearing potential

2.3 **REGISTRATION PROCEDURES**

Registration will be a two part process as patients are screened on this protocol. Authorized staff must register an eligible candidate with NCI Central Registration Office (CRO) within 24 hours of signing consent. To initially register a subject after the participant has signed the consent, complete the top portion the registration Eligibility Checklist from the website (http://home.ccr.cancer.gov/intra/eligibility/welcome.htm) indicating that the patient is being registered for screening and send via encrypted email to: NCI Central Registration Office [contact]. Once eligibility is confirmed after completion of Step 2 screening studies, complete the remainder of the form which is the eligibility checklist, indicating that the patient is being registered for treatment and email the completed registration checklist to the CRO at NCI Central Registration Office [contact]. After confirmation of eligibility at Central Registration Office, CRO staff will call pharmacy to advise them of the acceptance of the patient on the protocol prior to the release of any investigational agents. Verification of Registration will be forwarded electronically via e-mail to the research team. A recorder is available during non-working hours.

Subjects that do not meet screening criteria should be removed from the study following the procedure in section 3.5.3.

2.4 TREATMENT ASSIGNMENT AND RANDOMIZATION/STRATIFICATION PROCEDURES

Cohorts

Number	Name	Description
1	Safety Run-in Cohort,	The first 6 evaluable subjects enrolled in whom the higher of 2 de-escalating doses of anetumab ravtansine will be evaluated in order to determine the recommended phase 2 dose
2	Phase 2 Cohort	Subjects enrolled after the recommended Phase 2 dose has been determined

Arms

Number	Name	Description
1	Safety Run-in Arm	Subjects will be dosed with the higher of the 2 possible anetumab ravtansine doses (dose level 1) evaluated on the study
2	Phase 2 Arm	Subjects will be dosed with anetumab ravtansine at the recommended phase 2 dose (dose level 1 if no more than 1 DLT occurred in the safety run in arm, or at dose level -1 otherwise)

Stratifications

None

Randomization and Arm Assignment

This is not a randomized study. Subjects in Cohort 1 will be assigned directly to Arm 1. Subjects in Cohort 2 will be assigned directly to Arm 2.

2.5 **BASELINE EVALUATION**

Screening evaluations performed within 28 days prior and within 7 days prior to treatment initiation will be used as baseline.

3 STUDY IMPLEMENTATION

3.1 STUDY DESIGN

This is an open label, single center, phase I/II study of anetumab ravtansine in subjects with mesothelin positive lung adenocarcinoma. During the safety run-in portion of the study a recommended phase 2 dose (RP2D) will be determined in up to 2 dose levels of up to 6 patients each. In the phase 2 portion of the study, 20 evaluable subjects will be evaluated at the RP2D including the 6 subjects treated at this dose during the dose de-escalation study.

3.1.1 Study Schema

Safety Run-in

Abbreviated Title: Anetumab ravtansine in lung CA Version Date: 01-11-18

Treatment Schedule

3.1.2 Dose Limiting Toxicity

For the TEAEs of corneal epitheliopathy and the best corrected visual acuity (BCVA) changes potentially fulfilling the DLT criteria for anetumab ravtansine, the grading systems in Table 9 and Table 10 respectively_will be used. All other criteria will be assessed per section 6.4.2.

Any TEAE listed below occurring during Cycle 1 and regarded to be at least possibly related to anetumab ravtansine will represent a DLT for anetumab ravtansine treatment.

3.1.2.1 Hematological

- ANC <500/mm3 (CTCAE Grade 4) for \geq 7 days
- Febrile neutropenia (ANC < 1000/mm³ and a single body temperature reading of > 38.3°C (≥101 °F) or a sustained body temperature of ≥38.0 °C (≥100.4 °F) for more than 1 hour
- Platelet count < 25000/mm3 (CTCAE Grade 4) for ≥7 days regardless of the presence of active bleeding or platelet count <50000/mm³ (Grade ≥3) with clinically significant bleeding, i.e. bleeding requiring platelet transfusion

3.1.2.2 Non-hematological

• AST and/or ALT increase > 5.0 times ULN (CTCAE Grade \geq 3)

- AST and/or ALT increase > 3.0 times ULN (CTCAE Grade ≥ 2) with concomitant increase in total bilirubin >1.5 times ULN (CTCAE Grade ≥ 2)
- Total bilirubin > 3.0 times ULN (CTCAE Grade \geq 3)
- Grade ≥3 corneal epitheliopathy according to the Bayer severity grading for this type of TEAE (Table 9)
- Any other CTCAE Grade \geq 3 non-hematological toxicity **excluding** the following:
 - Nausea, vomiting, or diarrhea if manageable with antiemetic or antidiarrheal agents within 7 days
 - Hair loss
 - Fatigue lasting \leq 72 hours
 - Certain asymptomatic laboratory assessments without a clear clinical correlate, if the investigator determines that this TEAE should not be assessed a DLT.
 - CTCAE Grade ≥2 infusion reactions and other CTCAE Grade ≥2 hypersensitivity events deemed at least possibly related to anetumab ravtansine would not be considered a DLT, because hypersensitivity is not directly related to the dose. Nevertheless, these events would require treatment modification or discontinuation.
- Any other toxicity irrespective of the type or severity that represents a clinically significant risk to subject in the investigator's opinion.

If a medically important TEAE not listed above, which is at least possibly related to anetumab ravtansine, has been observed more frequently after Cycle 1, then this TEAE may be declared a DLT in the remainder of the study at the investigator's discretion.

3.1.3 Safety Run-in

The first 6 subjects will be enrolled at dose level 1. If <2 of 6 subjects experience a DLT, dose level 1 will be established as the RP2D and up to 20 evaluable subjects (including the first 6) will be enrolled at this dose level. If 2 or more subjects experience DLT at dose level 1, the RP2D is established at dose level -1 and up to 20 evaluable subjects will be enrolled at this dose level. If a patient did not experience DLT and did not finish treatment, he or she will not be evaluable for toxicity and will be replaced in the dose level. If at any time during the trial, the cumulative fraction of patients treated at the dose used in the phase II portion of the trial who have a DLT exceeds 1/3, then no further accrual will take place unless a treatment modification is provided via an amendment.

Table 3: Dose De-escalation Schedule	
Dose Level	Dose of anetumab ravtansine IV q 3 weeks
Level 1	6.5 mg/kg
Level -1	5.5 mg/kg

Number of Patients with DLT	De-escalation Decision Rule
at Dose Level	
0 or 1 out of 6	This will be the recommended phase 2 dose
$\geq 2 \text{ out of } 6$	The next lower dose level (DL -1) is established as the recommended phase 2 dose

Table 4	. Dece	de accelation	will follow	the wyles	autlined in	the	Table below	
Table 4	: Dose	ue-escalation	will follow	the rules	outimeu m	une	I able below.	

3.2 DRUG ADMINISTRATION

After reconstitution and dilution as described in section 11.1.3, anetumab ravtansine will be administered at a dose of 6.5 mg/kg or 5.5 mg/kg of body weight every 3 weeks as an intravenous infusion over 1 hour (+/- 15 minutes). **Note**: longer infusions are permitted if following dose modification guidelines; however, diluted anetumab ravtansine must be used within 6 hours. In obese patients, anetumab ravtansine dose should be calculated considering a maximum weight of 100 kg. Patients will continue on treatment until death, or occurrence of progressive disease (PD) in the absence of clinical benefit as defined by Response Evaluation Criteria in Solid Tumors (RECIST), version 1.1 (RECIST 1.1) or drug-related toxicity that requires discontinuation of treatment, or until another criterion for withdrawal from study is met.

3.3 DOSE MODIFICATIONS

Dose level 1 (starting dose):	6.5 mg/kg Q3W
Dose level -1	5.5 mg/kg Q3W
Dose level -2	4.5 mg/kg Q3W

3.3.1 Hematological toxicities

Dose modifications for hematological toxicity

- If treatment modification is required due to a hematological TEAE, and the continuation of treatment is appropriate, the anetumab ravtansine dose will be adjusted as described in Table 6 and Table 7 below.
- G-CSF and other hematopoietic growth factors may be used during the study in the management of acute toxicity such as febrile neutropenia when clinically indicated per ASCO Recommendations for Therapeutic Use of CSF¹⁷ or at the discretion of the investigator; however they may not be substituted for a required dose reduction.
- Blood transfusions and therapy with IV or subcutaneous erythropoietin-stimulating agents (epoetin alpha, darbepoetin alpha) are allowed per institution guidelines but may not be used as substitute for a required dose reduction (see also section 4.1).

• Platelet transfusion may be used during the study in the management of acute toxicity such as hemorrhage or bleeding events, however they may not be used as substitute for a required dose reduction.

Table 6	- Dose adjustments in	response to neutroph	nil and platelet nadir	^a counts of the
previous	cycle			

Absolute neutrophil nadir count of the previous cycle (/mm3)	Platelet nadir count of the previous cycle (/mm3)	Anetumab ravtansine dose adjustment ^b	
\geq 500 or < 500 for < 7 days and	≥ 25,000	No change	
$< 500 \text{ for} \ge 7 \text{ days}$ and/or	< 25,000 regardless of the presence of active bleeding (or \geq 25,000 with clinically significant bleeding, i.e. bleeding requiring platelet transfusion)	Decrease 1 dose level ^b	
Febrile neutropenia [°] and/or	< 25,000 regardless of the presence of active bleeding (or \ge 25,000 with clinically significant bleeding, i.e. bleeding requiring platelet transfusion)	Decrease 1 dose level ^b	

ANC = Absolute neutrophil count; C = Cycle; CBC = Complete blood count; D = Day; Q3W = Every 3 weeks

a) Clinic visits and blood test for CBC (and biochemistry) on D8 and D15 will be performed on C1, C2 and C3 only. From Cycle 4 onwards, visits and procedures on D8 and D15 are no longer required.

b) Dose reduction by 1 dose level translates to a change from 6.5 mg/kg Q3W to 5.5 mg/kg Q3W, or from 5.5 mg/kg Q3W to 4.5 mg/kg Q3W. Not more than 2 dose reductions from the starting dose level are permitted. c Febrile neutropenia is defined as ANC < 1000/mm3 and fever (a single body temperature reading of > 38.3°C [101°F] or a sustained body temperature of ≥ 38°C [100.4°F] for more than 1 hour).

Table 7 - Dose adjustments in response to pre-infusion values

Absolute neutrophil count (/mm ³)		Platelets (/mm ³)	Hemoglobin (g/dL)	Timing	Anetumab ravtansine dose adjustment
≥ 1,000	and	≥75,000		Treat on time	Adjust dose by nadir ^a counts in previous cycle per investigator's discretion
< 1,000	and/ or	< 75,000		Delay until ANC \geq 1.0 and platelets \geq 75,000 b	Decrease by 1 dose level ^c
			< 8	Delay until Hb $\geq 8^{b}$	Re-start at the same dose or decrease by 1

						dose level ^c (at investigator's discretion)
ANC =	Absolute n	eutrophil count;	C = Cycle; CBC =	Complete blood coun	t; $D = Day; Hb = H$	Iemoglobin; Q3W
= Every	3 weeks; T	EAE = Treatment	ent-emergent advers	se event		
a) Site visits and blood test for CBC (and biochemistry) on D8 and D15 will be performed on C1, C2 and C3 only. From Cycle 4 onwards, visits and procedures on D8 and D15 are no longer required.						
b) Treatment will be discontinued if the TEAE fails to resolve to Grade ≤ 1 (or Hb ≥ 9 g/dL in case of anemia) within 6 weeks after the last dose of anetumab ravtansine.						
c)	Dose redu 5.5 mg/kg permitted.	ction by 1 dose Q3W to 4.5 mg	level translates to a t/kg Q3W. Not mor	change from 6.5 mg/ e than 2 dose reduction	kg Q3W to 5.5 mg. ons from the startin	/kg Q3W, or from g dose level are

3.3.2 Non-hematological toxicities

3.3.2.1 Non-hematological toxicities requiring dose modification

- CTCAE Grade 2 anetumab ravtansine infusion-related reaction or other CTCAE Grade 2 hypersensitivity events (See section 3.3.3.2)
- AST and/or ALT increase $>5.0 \times ULN$ (CTCAE Grade ≥ 3)
- AST and/or ALT increase >3.0 x ULN (CTCAE Grade ≥ 2) with concomitant increase in total bilirubin >1.5 x ULN (CTCAE Grade ≥ 2)
- Total bilirubin \geq 3.0 x ULN (CTCAE Grade \geq 3)
- Bayer Grade \geq 3 corneal epitheliopathy (see below and Table 9)
- Any other Grade ≥ 3 non-hematological toxicity that, in the investigator's opinion, warrants treatment modification (see Table 8), **excluding** the following:
 - Nausea, vomiting, or diarrhea if manageable with anti-emetics or anti- diarrheals within 7 days
 - Hair loss
 - \circ Fatigue lasting \leq 72 h
- Any other toxicity irrespective of the type or severity that represents a clinically significant risk to patient in the investigator's opinion.

3.3.2.2 Dose modifications for non-hematological toxicity

If treatment modification is required due to Grade ≥ 3 non-hematological TEAE, other than corneal epitheliopathy and infusion-related reaction/hypersensitivity events, and the continuation of treatment is appropriate, the anetumab ravtansine dose will be either reduced or maintained as is at investigator's discretion (see Table 8).

Table 8 - Dose adjustments in response to non-hematologic toxicities

CTCAE v4.0 grade	Anetumab ravtansine dose delay / interruption	Anetumab ravtansine dose modification
Grade $1 - 2^{a}$	Treat on time	No change required

CTCAE v4.0 grade	Anetumab ravtansine dose delay / interruption	Anetumab ravtansine dose modification
Grade 3	1st appearance: Delay /Interruption until Grade $\leq 2^{b}$	Re-start at the same dose or decrease by 1 dose level ^c (at investigator's discretion)
	2nd appearance: Delay /Interruption until Grade $\leq 2^{b}$	Decrease by 1 more dose level ^c
	3rd appearance: Permanently discontinue	
Grade 4	Permanently discontinue	

ALT = Alanine aminotransferase; AST = Aspartate aminotransferase; CTCAE = Common Terminology Criteria for Adverse Events; Q3W = Every 3 weeks; TEAE = Treatment-emergent adverse event

- a) AST and/or ALT increase of CTCAE Grade 2 with concomitant increase in total bilirubin of CTCAE Grade 2 will be treated as a CTCAE Grade 3 event.
- b) Treatment will be discontinued if the TEAE fails to resolve to Grade ≤ 1 within 6 weeks after the last dose of anetumab ravtansine.
- c) Dose reduction by 1 dose level translates to a change from 6.5 mg/kg Q3W to 5.5 mg/kg Q3W, or from 5.5 mg/kg Q3W to 4.5 mg/kg Q3W. Not more than 2 dose reductions from the starting dose level are permitted.

The anetumab ravtansine dose reduction due to non-hematological TEAE will be done as described below:

- If the patient experienced a TEAE requiring dose reduction at the 6.5 mg/kg Q3W dose level, the subsequent anetumab ravtansine dose should be reduced to 5.5 mg/kg Q3W.
- If the patient experienced a TEAE requiring dose reduction at the 5.5 mg/kg Q3W dose level, the subsequent anetumab ravtansine dose should be reduced to 4.5 mg/kg Q3W.

After dose reduction for TEAE, there could be no intra-patient dose re-escalation irrespective of the type of TEAE that has led to dose reduction in this patient with the exception of grade 3 corneal epitheliopathy as per Table 9.

3.3.3 Miscellaneous toxicities

3.3.3.1 IV infusion-related reaction and other hypersensitivity events

If a patient experiences a CTCAE Grade 2 anetumab ravtansine infusion reaction or other CTCAE Grade 2 hypersensitivity event deemed at least possibly related to anetumab ravtansine, the infusion of anetumab ravtansine will be interrupted.

If treatment interruption is caused by a CTCAE Grade 2 anetumab ravtansine **infusion-related reaction or other CTCAE Grade 2 hypersensitivity event** deemed at least possibly related to anetumab ravtansine, treatment may be re-started at the time determined at the investigator's discretion. Re-treatment should be at the infusion rate reduced by 50%, along with anti-allergic prophylaxis (e.g. anti-histamines, acetaminophen, and/or corticosteroids) chosen at the investigator's discretion or according to the institutional guidelines.

In case of a CTCAE Grade \geq 3 hypersensitivity and acute infusion reaction, treatment must be permanently withdrawn.

3.3.3.2 Miscellaneous toxicities requiring dose modification

For any toxicity \leq Grade 2 assessed as related to anetumab ravtansine by the investigator, dose modification should be considered. Such toxicities might be \leq Grade 2 toxicities which interfere with the activities of daily life, such as long lasting fatigue, or anorexia, or corneal epitheliopathy with vision impairment etc. A dose change might be necessary in order to ensure the patient's compliance. These toxicities may be declared "TEAE requiring treatment modification" after per investigator discretion.

3.3.3.3 Dose modifications for corneal epitheliopathy

For the TEAE of corneal epitheliopathy and the best corrected visual acuity (BCVA) changes (blurred vision), the Bayer severity grading system (see Table 9 and Table 10) will be used to assess the severity of TEAEs requiring modification of anetumab ravtansine treatment.

TEAE of corneal epitheliopathy deemed to be at least possibly related to anetumab ravtansine would require modification of anetumab ravtansine treatment (dose reduction or permanent discontinuation of treatment) according to the following principles (see Table 9).

	Grade 0	Grade 1	Grade 2	Grade 3	Grade 4
Corneal morphology	No pathologic changes	Any stage of superficial punctate keratitis ^a	Epithelial opacities Micro-cysts Micro-deposits Corneal erosion Stromal opacity: non-central	Corneal ulcer without risk of acute rupture Stromal opacity: central	Corneal ulcer more severe than Grade 3
Eye treatment ^b	Ocular lubricants at the discretion of investigator in consultation with ophthalmologist/ optometrist	Ocular lubricants; add topical steroids if superficial punctate keratitis shows treatment- emergent progression by ≥ 2 SPK Grades	Intensive treatment with ocular lubricants enhanced with ointments; topical steroids; therapeutic contact lens may be considered at the discretion of investigator in consultation with ophthalmologist/ optometrist	Intensive therapy with ointments; topical steroids; therapeutic contact lens or occlusion recommended at the discretion of investigator in consultation with ophthalmologist /optometrist	Intensive therapy with lubricants, ointments, topical steroids and antibiotics as needed; occlusion or therapeutic contact lens recommended; amniotic membrane transplant and other locally approved therapies to be considered at the discretion of investigator in consultation with ophthalmologist / optometrist

Table 9 -	- Baver	classification	and manage	ement of corne	al epitheliop	athv
	,					

	Grade 0	Grade 1	Grade 2	Grade 3	Grade 4
Anetumab ravtansine ^c	No change	No change	Keep treatment dose level and schedule if the ophthalmological exam can be performed as needed; otherwise consider dose reduction by -1 dose level without dose schedule change at the discretion of investigator in consultation with ophthalmologist/ optometrist	1) Decrease dose to -1 dose level (or -2 dose level if event does not resolve to Grade ≤ 2 at the -1 dose level within 3 weeks) 2) Re-start at the original dose level if the first Grade 3 event resolves to Grade ≤ 2 within 3 weeks and does not recur 3) If not resolved within	Discontinue treatment
				resolved within 3 weeks continue at reduced -1 dose level (or -2 dose level)	

Abbreviated Title: Anetumab ravtansine in lung CA Version Date: 01-11-18

SPK = Superficial punctate keratitis

a) Oxford Schema must be used for grading SPK from stage 0 to VI.

- b) Other remedial therapies for corneal epitheliopathy may be added or substituted at investigator's discretion or according to the institutional standards.
- c) Treatment decisions are based on corneal epitheliopathy only, not on visual acuity changes.

Table 10 - Bayer classification of visual acuity changes

	Grade 0	Grade 1	Grade 2	Grade 3	Grade 4
Visual acuity	No findings, no reporting from the patient	Symptomatic visual acuity loss < 3 lines (ETDRS equivalent ^a)	Visual acuity loss \geq 3 lines, but < 6 lines (ETDRS equivalent ^a)	Visual acuity loss \geq 6 lines, (ETDRS equivalent ^a)	Visualacuityloss \geq 6 lines,(ETDRSequivalent ^a)leadingtoblindness

ETDRS = Early Treatment Diabetic Retinopathy Study

a) In the ETDRS chart, each loss of 3 lines corresponds to halving the visual acuity. In other charts, an equivalent amount of visual acuity loss must be reached in order to meet this threshold.

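### Table 9's Grade 3 corneal rule uses level names that fit only an event starting at 6.5 mg/kg; for one starting at 5.5 mg/kg the literal text gives no first reduction

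*Combined protocol and SAP*

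**What the plan says.** Section 3.3 sets a ladder of named levels. "Dose level 1 (starting dose") is 6.5 mg/kg every 3 weeks, level -1 is 5.5 mg/kg and level -2 is 4.5 mg/kg. No lower level is listed. Section 3.1.3 makes 5.5 mg/kg a planned phase 2 dose: "If 2 or more subjects experience DLT at dose level 1, the RP2D is established at dose level -1".

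Table 9 in section 3.3.3.3 governs corneal events. Its Grade 3 cell has three steps:

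1. "Decrease dose to -1 dose level (or -2 dose level if event does not resolve to Grade" 2 or lower at level -1 within 3 weeks).
2. Return to the original dose if the first Grade 3 event settles to Grade 2 or lower within 3 weeks and does not come back.
3. If it has not settled: "resolved within 3 weeks continue at reduced -1 dose level (or -2 dose level").

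The Grade 2 cell beside it is worded as a relative step: "otherwise consider dose reduction by -1 dose level without dose schedule change".

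Elsewhere a one-level reduction is always a step from the current dose. Footnote b to Table 6 reads "Dose reduction by 1 dose level translates to a change from 6.5 mg/kg Q3W to 5.5 mg/kg Q3W", or from 5.5 to 4.5 mg/kg, and the footnotes to Tables 7 and 8 repeat this. Section 3.3.2.2 gives the same steps in mg/kg for non-hematological events. Section 3.3.5 calls 4.5 mg/kg the minimum dose and requires permanent discontinuation if a reduction is needed there.

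**The concern.** The Grade 3 cell says to go *to* a named level, whereas the rest of the dose-modification section goes down *by* a level. The two agree only for a patient at 6.5 mg/kg. At 5.5 mg/kg, going to level -1 is no change.

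Patients can be at 5.5 mg/kg when a Grade 3 corneal event starts by two routes: it became the phase 2 dose after the run-in, or they started at 6.5 mg/kg and were reduced for a different toxicity.

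Grade 3 in Table 9 means a corneal ulcer without risk of acute rupture, or a central stromal opacity. Section 1.2.3.1 relates the probability of corneal epitheliopathy to drug exposure, expects dose reduction to lower it, and names corneal toxicity among the commonest reasons for dose changes at 6.5 mg/kg. The first reduction is therefore the main protective step. It should be readable from the cell that governs it, because section 3.3.3.3 sends the clinician to Table 9.

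**Working it through.** **1. Apply the cell to the section 3.3 ladder.**

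| Dose when the Grade 3 event starts | Table 9 step 1, named level | Table 9 fallback, named level | First step under Tables 6 to 8 footnotes and section 3.3.2.2 |
|---|---|---|---|
| 6.5 mg/kg | 5.5 | 4.5 | 5.5 |
| 5.5 mg/kg | 5.5 (no change) | 4.5 | 4.5 |

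The rows agree at 6.5 mg/kg and disagree at 5.5 mg/kg.

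**2. Can the intended step be inferred?** Largely, yes.

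- Section 3.3.3.3 says a drug-related corneal event "would require modification of anetumab ravtansine treatment (dose reduction or permanent discontinuation of treatment"). Leaving the dose at 5.5 mg/kg is neither.
- Section 3.3.2.1 lists Bayer Grade 3 or higher corneal epitheliopathy among the non-hematological toxicities requiring modification.
- Section 3.3.2.2 gives the 5.5 to 4.5 mg/kg step for non-hematological events, then bars re-escalation except after Grade 3 corneal epitheliopathy. That exception makes most sense if the mg/kg steps cover corneal reductions.
- Against this, section 3.3.2.2 opens by setting corneal epitheliopathy aside, so whether its steps control a Table 9 event can be argued.

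**3. Size of the departure if the cell is followed literally.** Take a single Grade 3 event starting at 5.5 mg/kg, with 5.5 mg/kg as the original dose in step 2.

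- Resolves within 3 weeks: literal text, 5.5 throughout; inferred rule, one infusion at 4.5, then back to 5.5.
- Does not resolve: literal text, one more infusion at 5.5, then 4.5; inferred rule, 4.5 at once.

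Either way the difference is about one infusion. Relative dose = 5.5/4.5 = 1.222, about 22% higher; equivalently, a cut of 1.0/5.5 = 18.2% is not made. Section 1.2.3.1 reports roughly dose-proportional exposure from 0.15 to 7.5 mg/kg, so the AUC excess for that cycle is also about 22%.

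**4. Is 5.5 mg/kg a remote branch?** It becomes the phase 2 dose if at least 2 of 6 patients have a DLT. With DLT probability p, P = 1 − (1 − p)^6 − 6p(1 − p)^5. The documents give no p for this population, so p is an assumption: P = 0.11 at 10%, 0.35 at 20%, 0.58 at 30% and 0.77 at 40%.

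**5. Background frequency.** At 6.5 mg/kg every 3 weeks, 11 of 38 patients had any corneal event: 28.9%, exact 95% CI 15.4% to 45.9%. None was serious and all were reversible. Table 11 shows no drug-related blurred vision, corneal disorder or corneal microcysts in escalation cohorts 1 to 8A (3+3+4+4+4+4+4+9 = 35 patients), of whom 9 received 5.5 mg/kg. No Bayer Grade 3 rate is given, so I do not estimate a number of affected patients.

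**The case against.** The strongest reply is that the cell should not be read alone. Section 3.3.2.2 states the 5.5 to 4.5 mg/kg step, an instruction to decrease cannot sensibly mean staying at the same dose, and section 3.3.5 sets the floor. On that view this is one wrong preposition. Most of this stands: the intended first step can be recovered, and a careful investigator would probably take it. What does not go away is that section 3.3.2.2 opens by excluding corneal epitheliopathy, so its authority over Table 9 is arguable, and that the table governing corneal events names the wrong dose for a planned starting level.

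A reader might go further and infer that the protocol sends such a patient to 3.5 mg/kg, by reading the levels as relative and subtracting two 1 mg/kg steps from 5.5 mg/kg. The cap of two reductions from the starting dose invites the same arithmetic. The documents do not support it: 3.5 mg/kg appears nowhere as a level, the section 3.3 ladder ends at 4.5 mg/kg, and section 3.3.5 makes that the minimum.

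It would also overstate the point to count every patient reduced from 6.5 to 5.5 mg/kg. If that reduction was for the same unresolved Grade 3 corneal event, the cell works as written, because level -2 is then 4.5 mg/kg.

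**Conclusion.** Wrong as written, minor. For a Grade 3 corneal event that starts at 5.5 mg/kg, the literal instruction makes no first reduction and conflicts with the step defined elsewhere in section 3.3. The documents do not support the stronger conclusion that the protocol as a whole provides no reduction for these patients.

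The practical effect is about one 3-week cycle at 5.5 instead of 4.5 mg/kg. This assumes one Grade 3 event, literal reading of the cell, and dose-proportional exposure; a recurrence at 5.5 mg/kg would lengthen it. The study calendar (section 3.4, footnote 4) repeats slit lamp and visual acuity before every infusion after the first, which limits the delay. No sample size, decision rule or other statistical figure depends on this cell.

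**What to change.** Restate the Grade 3 cell in mg/kg.

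- Step 1: *Decrease by one dose level from the current dose (6.5 to 5.5, or 5.5 to 4.5 mg/kg). If not resolved to Grade 2 or lower within 3 weeks, decrease one further level where one exists. 4.5 mg/kg is the minimum dose and section 3.3.5 applies.*
- Step 3: *If not resolved within 3 weeks, continue at the reduced dose reached, subject to section 3.3.5.*

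The rewording should not add a 3-week stopping rule for patients who go from 5.5 to 4.5 mg/kg. That would be new clinical policy: it would conflict with step 3, which continues treatment at the reduced level, and would treat them differently from patients who reach 4.5 mg/kg from a 6.5 mg/kg start.

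The cost is an edit to one table cell, with no added visits, procedures or patients and no change to the statistical section.

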3.3.5 Permanent discontinuation of anetumab ravtansine due to TEAEs

- CTCAE Grade 4 non-hematological AE and Bayer Grade 4 corneal epitheliopathy (see Table 9) (except at the investigator's discretion in case of certain Grade 4 abnormality of laboratory assessments, such as abnormal laboratory assessments without corresponding clinical symptoms, or abnormal laboratory assessments that can be easily clinically managed).
- If any type of TEAE requiring dose modification does not resolve to Grade ≤ 1 (or Hb ≥ 9 g/dL in case of anemia) within 6 weeks after the last dose of anetumab ravtansine.
- Delay in anetumab ravtansine administration of 3 weeks (max. 6 weeks between 2 infusions of study drug).
- TEAE requiring dose reduction when already at the 4.5 mg/kg Q3W dose level (minimum dose).
- More than 2 dose reductions required due to a TEAE.

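### Table 9 continues an unresolved Grade 3 corneal event at 4.5 mg/kg without limit, and the protocol does not say whether Table 9 or the stops in 3.3.5 govern

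*Combined protocol and SAP*

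**What the plan says.** Section 3.3.3.3 states that a related corneal event leads to "dose reduction or permanent discontinuation of treatment) according to the following principles" set out in Table 9. The Grade 3 column, whose findings are "Corneal ulcer without risk of acute rupture Stromal opacity: central", has three items.

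- Item 1: "Decrease dose to -1 dose level (or -2 dose level if event does not resolve to Grade" 2 or lower within 3 weeks at -1.
- Item 2: "Re-start at the original dose level if the first Grade 3 event resolves to Grade" 2 or lower within 3 weeks and stays resolved.
- Item 3, for an event that does not resolve: "resolved within 3 weeks continue at reduced -1 dose level (or -2 dose level".

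Only the Grade 4 column tells the investigator to discontinue. Section 3.3 sets dose level -1 at 5.5 mg/kg and -2 at 4.5 mg/kg.

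Section 3.3.5 lists the permanent stops. Four bear on this point.

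- Bullet 1 begins "CTCAE Grade 4 non-hematological AE and Bayer Grade 4 corneal epitheliopathy (see" and names no other corneal grade.
- Bullet 2 begins "If any type of TEAE requiring dose modification does not resolve to Grade" 1 or lower. It allows 6 weeks, counted from the last dose, a term it does not define. It makes no exception for Grade 3 corneal events.
- Bullet 3 is "Delay in anetumab ravtansine administration of 3 weeks (max. 6 weeks between 2 infusions of study drug").
- Bullet 4 stops treatment when a TEAE calls for a reduction and the patient is already at the 4.5 mg/kg minimum.

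Section 3.3.2.1 lists Bayer Grade 3 or higher corneal epitheliopathy among the toxicities that require dose modification, so bullet 2 covers it. Section 3.3.4 permits re-start only once the TEAE is at Grade 2 or lower within 6 weeks of the last dose.

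**The concern.** Table 9 item 3 and section 3.3.5 give opposite instructions for the same patient. One continues at the lowest dose with no end point. The other ends treatment, at a time that depends on which bullet is applied and how last dose is read. No sentence says which rule prevails.

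Bayer Grade 3 is a serious finding in the eye, and section 1.2.3.1 reports drug exposure as a descriptor of corneal epitheliopathy, so extra infusions matter. Two investigators who both follow the text could differ: one stops at week 6 and the other keeps dosing.

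Other protections remain. They are the slit-lamp examination before each infusion after the first (section 3.4, footnote 4), eye-specialist consultation, the Grade 4 stop, and removal at investigator discretion (3.5.1). A Grade 3 event in Cycle 1 also counts as a DLT in the run-in and toward the one-third accrual stop. None of these settles which rule applies to a persistent Grade 3 event. The unacceptable-toxicity criterion in 3.5.1 refers back to section 3.3, so it inherits the same ambiguity.

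**Working it through.** The plan gives no figure to reproduce. The check sets the rules side by side and counts weeks on the 3-week cycle.

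**Assumed case.** Week 0 is the last dose before onset. Grade 3 is found at the week 3 pre-infusion examination and does not resolve. Infusions stay on schedule. Week 12 is an arbitrary cut-off for comparison. For a patient who starts at 5.5 mg/kg (the phase 2 dose if 2 or more of the first 6 have a DLT), the first reduction is taken as 4.5 mg/kg, as in 3.3.2.2.

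Start at 6.5 mg/kg:

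| Week | Table 9 alone | 3.3.5 bullet 2, counted from week 0 | 3.3.5 bullet 4, applied at 4.5 mg/kg |
|---|---|---|---|
| 3 | 5.5 | 5.5 | 5.5 |
| 6 | 4.5 | stop | 4.5 |
| 9 | 4.5 | – | stop |
| 12 | 4.5 | – | – |
| Total | 5.5 + 3 × 4.5 = 19.0 mg/kg, no stop | 5.5 mg/kg | 5.5 + 4.5 = 10.0 mg/kg |

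Start at 5.5 mg/kg: Table 9 alone gives 4 × 4.5 = 18.0 mg/kg by week 12 with no stop. Bullets 2 and 4 each give one infusion of 4.5 mg/kg and stop at week 6.

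**Two readings of last dose in bullet 2.**

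- Dose before onset: the 6 weeks end at week 6. For a patient who started at 6.5 mg/kg, that is the visit at which Table 9 orders the first 4.5 mg/kg dose, so the two rules collide.
- Most recent infusion: the interval is 3 weeks on schedule, or 3 + 2 = 5 weeks with the full scheduling delay in section 3.4. Both are below 6, so the rule is not reached while dosing continues. If dosing is withheld, bullet 3 reaches its own limit at 3 + 3 = 6 weeks.

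**Minimum-dose stop.** If Grade 3 at 4.5 mg/kg counts as requiring a reduction, bullet 4 stops treatment on either reading, and item 3 contradicts it by saying to continue. If it does not count, because item 3 says to continue, bullet 4 does not apply.

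**Re-start.** A persistent Grade 3 event fails the Grade 2 condition in 3.3.4. Table 9 states no hold for Grade 3. Item 2 speaks of re-starting, but item 1 speaks of resolution while at the -1 dose. Whether 3.3.4 applies is therefore unclear.

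**Item 2 against bullet 2.** Item 2 needs Grade 2 or lower by 3 weeks, and bullet 2 needs Grade 1 or lower by 6 weeks. They can run in sequence and collide only if the eye is still at Grade 2 at week 6.

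**How many patients.** Section 1.2.3.1 reports corneal events of any grade in 11/38 = 28.9% at 6.5 mg/kg (exact 95% interval 15.4% to 45.9%), none serious and all reversible. It gives no count of persistent Grade 3. If that count is assumed to be 0 of 38, the upper 95% limit is 1 − 0.025^(1/38) = 9.25%. For 20 patients the range is 0 to 20 × 0.0925 = 1.85, or about 2.

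**The case against.** The best defence is that Table 9 is the specific rule. Section 3.3.3.3 sends corneal events to it, 3.3.2.2 takes them out of Table 8, and bullet 1 of 3.3.5 names only Grade 4. Continued reduced dosing under specialist eye care may be deliberate. That reading is possible but not stated. Where the authors wanted Table 9 to override a general rule they said so: 3.3.2.2 bars re-escalation except for Grade 3 corneal epitheliopathy. Bullet 2 has no such exception. If Table 9 does govern alone, a persistent Grade 3 event has no set stop.

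A second defence is that counting from the most recent infusion leaves bullet 2 with little effect, so the dose before onset is the natural reading. If dosing is held, the two readings coincide. This has force, but that reading is the one that collides directly with item 1.

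A reader might also infer that the protocol has no stop at all for a persistent Grade 3 event. The documents do not support that. Section 3.3.3.3 names reduction or discontinuation as the responses, 4.5 mg/kg is the minimum, and bullet 4 can be applied there. Bullet 2 also stops treatment on one reading. The defect is that Table 9 contradicts usable stops. Nor does item 2 conflict with bullet 2 in general, as the sequence above shows.

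The expected frequency is low and the week 12 totals depend on the chosen cut-off. Both points stand.

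**Conclusion.** Table 9, Grade 3, item 3 is not reconciled with bullets 2 and 4 of 3.3.5 or with 3.3.4, and the text does not say which governs. For a patient who started at 6.5 mg/kg and has a persistent event, the rules give one infusion, two, or dosing with no set end. From 5.5 mg/kg they give one infusion or no set end.

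This is a patient-safety clarification that should be made. It does not touch the response endpoint or the two-stage design. Few patients are likely to be affected: up to about 2 of 20 on the assumption of 0 of 38 above, a count that the documents do not report. The comparison of rules rests on the text alone. The infusion counts also rest on the assumed timeline.

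**What to change.** Make two changes by amendment.

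1. Add to Table 9, Grade 3, item 3: *Permanently discontinue if the event has not resolved to Grade ≤2 within 3 weeks at 4.5 mg/kg, or if Grade 3 recurs at 4.5 mg/kg (3.3.5, minimum dose).* Stating the limit in mg/kg makes it work for either starting dose. The sponsor's ophthalmology advisers should confirm the interval.
2. In 3.3.5 bullet 2, state that the dose steps for a Grade 3 corneal event follow Table 9 while the patient is above 4.5 mg/kg, define last dose, and keep the other 3.3.5 stops in force for corneal events. The definition must leave the 4.5 mg/kg step usable: a 6-week count from the dose before onset, applied without this wording, would remove that step for a patient who started at 6.5 mg/kg.

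The cost is a few sentences, with no added procedures or patients. There are two clinical consequences. A few patients with persistent Grade 3 events stop earlier than under Table 9 alone. A patient who started at 6.5 mg/kg may receive one more reduced infusion than under bullet 2 counted from the dose before onset (2 infusions, 10.0 mg/kg, against 1 infusion, 5.5 mg/kg). The wider difference between Grade 2 in 3.3.4 and Grade 1 in 3.3.5 applies to all toxicities, and this change does not resolve it.
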